#### **4.4.1.2 Additional Efficacy Analyses Focused on Refill Times**

The following endpoints will be summarized using descriptive statistics and 80% CIs. These analyses will be done using the modified ITT population observed data.

- Time to subsequent Implant refills according to protocol-defined refill criteria will be estimated using the Kaplan-Meier method.

Time from first refill to the second refill will be analyzed for patients who have undergone the first refill, do not receive an intravitreal anti-VEGF injection in the study eye prior to the first refill, and do not have visits prior to the first refill where refill criteria cannot be adequately assessed.

Time from the first refill to the second refill is defined as time from the date of the first refill to the date of the second refill. For patients who do not have the second refill prior to or on the cutoff date, time to second Implant refill will be censored on the date of a patient's last visit before the cutoff date or the date when the patient discontinues from the study, whichever occurs first.

Time to second Implant refill will also be censored for the following patients:

- At the time of an intravitreal anti-VEGF injection in the study eye if administered before the second refill
- At the time the refill criteria cannot be adequately assessed, which is defined as at least two refill variables (BCVA, CFT, or new macular

hemorrhage) cannot be evaluated for any reason, or are affected by a clinical reason different from nAMD activity, before the second refill

- At the time of explant

Similar approach will be used to define time from the second refill to the third refill, etc.

- Total number of times a patient meets protocol-specified refill criteria and is refilled will be provided over the following time intervals first 5 months, from Month 6 to Month 10, greater than 10 months
- Patient listing of dosing errors and refill time errors
- Percentage of patients not meeting the protocol-defined first refill criteria over time, derived from Kaplan-Meier estimates

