**Figure 1 Study Schema**

D1=Day 1; ITV=intravitreal; LPI=last patient in; M1=Month 1; M9=Month 9; PA=primary analysis; PD=ranibizumab port delivery; PRN=as needed (as per the refill criteria); RBZ=ranibizumab; SOC=standard-of-care.

Note: Ranibizumab filled Implant inserted (Day 1).

The study will include screening and randomization visits followed by a treatment period. Baseline measurements will be taken at the randomization visit. The patients will then be randomized to a treatment arm using a permuted block randomization scheme stratifying by best corrected visual acuity (BCVA) score ( $\leq 65$  letters vs.  $\geq 66$  letters) and number of prior anti-VEGF intravitreal injections ( $\leq 3$  vs.  $\geq 4$ ).

Patients randomized to the Implant treatment arms will have the Implant (prefilled with ranibizumab) surgically inserted in the study eye at their Day 1 visit, after which they will be evaluated monthly for the need for an Implant refill based upon protocol-specified-refill criteria for the remainder of the study treatment duration. Patients randomized to the intravitreal injection treatment arm (control) will be treated monthly with intravitreal injections of ranibizumab, starting at their Day 1 visit and continuing for the remainder of the study treatment duration.

The study had specific criteria for refill, rescue, and lack of clinical efficacy (LCE), which are provided below.

**Refill Criteria:** The patients randomized to the Implant treatment arms will have their Implant refilled only if any of the following criteria is met, as automatically determined by contacting interactive voice/Web response system (IxRS):

- Increase in central foveal thickness (CFT) of  $\geq 75$   $\mu\text{m}$  on spectral domain optical coherence tomography (SD-OCT) at the current visit compared with the average CFT over the last 2 available measurements, due to nAMD disease activity  
OR
- Increase in CFT of  $\geq 100$   $\mu\text{m}$  from the lowest CFT measurement on study, due to nAMD disease activity  
OR
- Decrease of  $\geq 5$  letters in BCVA at the current visit compared with the average BCVA over the last two available measurements, due to nAMD disease activity  
OR
- Decrease of  $\geq 10$  letters from best recorded BCVA on study, due to nAMD disease activity  
OR
- Presence of new macular hemorrhage, due to nAMD disease activity.

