**Rescue Criteria:** Rescue treatment with open-label ranibizumab (0.5 mg intravitreal injections of 10 mg/mL formulation) for patients in the Implant arm is allowed only under the following circumstances:

- Approximately 1 month and/or 2 months after occurrence of vitreous hemorrhage, if vitreous hemorrhage causes loss in BCVA, and neither assessment of the macula nor SD-OCT can be performed successfully.
- At the time a patient meets criteria for LCE (see below).
- In the case of progressive worsening of BCVA and/or CFT due to wet AMD activity across two consecutive scheduled visits, only if the patient does not meet refill criteria. If a treatment is clinically necessary due to the progressive clinical worsening per the investigator's judgment, rescue treatment must be discussed and agreed upon by the Medical Monitor prior to being introduced.

**Lack of Clinical Efficacy Criteria:** If a study patient randomized to the Implant treatment arm meeting criteria for LCE, he or she will receive a rescue injection with open-label ranibizumab at the time of meeting LCE. In addition, he or she will receive a mandatory refill at the 100 mg/mL formulation one month after the rescue intravitreal injection. After that, the 100 mg/mL formulation will be used for all future refills, whenever the patient meets refill criteria. The LCE criteria are as follows:

- Loss in BCVA of  $\geq 15$  letters from the best recorded BCVA on study following two consecutive ranibizumab Implant refills (as per protocol-specified refill criteria)

occurring 1 month apart due to nAMD disease activity and not attributable to a change in the ocular media (i.e., cornea, lens, aqueous or vitreous humor, epiretinal membrane development, etc.) unless there is at least a five-letter increase in BCVA, in which case a refill will occur.

and/or

- Increase in CFT  $\geq 150$   $\mu\text{m}$  from the lowest CFT measurement on study following two consecutive ranibizumab Implant refills (as per protocol-specified refill criteria) occurring 1 month apart due to nAMD disease activity and not attributable to a change in the ocular media (i.e., cornea, lens, aqueous or vitreous humor, epiretinal membrane development, etc.) unless there is a decrease in CFT  $\geq 75$  microns from the last refill, in which case a refill will occur.

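### From the second-to-third refill interval on, the subsequent-refill analysis censors lack-of-clinical-efficacy patients at a visit where they meet the refill criteria, so refill-free estimates are biased upward

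*SAP*

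**What the plan says.** **Endpoint.** SAP 4.4.1.2 states: "Time to subsequent Implant refills according to protocol-defined refill criteria will be estimated using the Kaplan-Meier method". The operative definition uses refill dates. The first interval "is defined as time from the date of the first refill to the date of the second refill".

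**Censoring.** In that first-to-second interval a patient is also censored "At the time of an intravitreal anti-VEGF injection in the study eye if administered before the second refill". Entry requires that no such injection was given before the first refill. For later intervals the SAP gives only this: "Similar approach will be used to define time from the second refill to the third refill, etc".

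**Refill criteria (SAP 2; Protocol 3.1.1).** Among other routes, a refill is due when BCVA has fallen by 10 or more "letters from best recorded BCVA on study, due to nAMD disease activity", or when CFT has risen by 100 µm or more from its lowest on-study value for the same reason.

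**LCE criteria (SAP 2; Protocol Table 7).** The BCVA limb is a loss of 15 or more "letters from the best recorded BCVA on study following two consecutive ranibizumab Implant refills (as per protocol-specified refill criteria", those refills being one month apart. The CFT limb is a rise of 150 µm or more from the lowest on-study value, with the same two-refill condition. Both must be due to nAMD activity. The BCVA limb has an exception: "unless there is at least a five-letter increase in BCVA, in which case a refill will occur". The CFT limb has a parallel one for a fall of at least 75 µm.

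**Treatment at LCE (SAP 2; Protocol 5.1.1.3 and Table 8).** On meeting LCE, "he or she will receive a rescue injection with open-label ranibizumab at the time of meeting LCE". A mandatory refill follows one month later.

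**The concern.** The analysis is meant to show how long later fills last before the refill criteria are met again. A patient whose disease has worsened past those criteria, despite two refills a month apart, is removed without an event because a different treatment was given that day. The ordering is odd. A patient 15 letters below best who has regained five is refilled and counts as an event; one who has regained nothing is rescued and censored. Elsewhere the SAP treats rescue as bad news: the trimmed-mean BCVA analysis in 4.4.2.1 ranks implant patients rescued before Month 9 among the worst outcomes.

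Kaplan-Meier estimation assumes that censored patients have the same subsequent refill hazard as those still under observation. Here the censoring is triggered by the outcome, so the assumption fails. What is at stake is the description of how durable later fills are.

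**Working it through.** **1. Does every LCE visit meet the refill criteria?** The two sets use the same references and the same attribution to nAMD.

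| Measure | Reference | Refill | LCE |
|---|---|---|---|
| BCVA loss | best on study | ≥10 letters | ≥15 letters |
| CFT rise | lowest on study | ≥100 µm | ≥150 µm |

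A loss of 15 letters is at least 10, and a rise of 150 µm is at least 100. A grid over BCVA losses of 0–60 letters and CFT rises of 0–400 µm found no state that meets LCE but not the refill criteria.

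**2. In which interval can LCE censor?** LCE needs two prior refills, so the earliest interval is second-to-third. The line about injections before the second refill captures no LCE patient. The sentence extending the approach does.

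**3. What happens to the mandatory refill?** It falls a month after the censoring date, so it is not counted. By analogy with the stated entry rule, the earlier injection also keeps the patient out of later intervals.

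**4. The plan's only sizing figure for a refill-time endpoint.** SAP 2.3 gives 85 events, about 80% power, HR 0.66, one-sided 15%, for time to first refill. With z(0.85) = 1.036 and z(0.80) = 0.842, the squared sum is 3.527.

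- Freedman: 3.527 × (1.66/0.34)² = 84.1, so 85 events, which matches.
- Schoenfeld: 4 × 3.527/(ln 0.66)² = 81.7, so 82 events. Power at 85 events is 81.0%.

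LCE cannot precede the first refill, so none of this changes. The subsequent-refill analysis has no stated size, power or LCE rate.

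**5. Size of the bias (illustration).** Assume a fraction f of patients entering the interval meets LCE at its first monthly visit, a fraction d of the others refills then, and the monthly refill hazard afterwards is d. Events precede censorings at ties.

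- As planned: S(3) = [1 − (1 − f)d] × (1 − d)²
- LCE visit as event: S(3) = (1 − f)(1 − d) × (1 − d)²

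With d = 0.20, (1 − d)² = 0.64:

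| f | As planned | LCE as event | Excess |
|---|---|---|---|
| 0% | 0.80 × 0.64 = 0.512 | 0.80 × 0.64 = 0.512 | 0 |
| 5% | 0.81 × 0.64 = 0.518 | 0.76 × 0.64 = 0.486 | 3.2 points |
| 10% | 0.82 × 0.64 = 0.525 | 0.72 × 0.64 = 0.461 | 6.4 points |

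**6. A second set of assumptions.** Let 15% of all entrants refill at the first visit, with a 15% monthly hazard afterwards. The planned estimate is 85.0% at 1 month and 0.85 × 0.85⁵ = 37.7% at 6 months, whatever the LCE share. With the LCE visit as an event:

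- LCE share 5%: 80.0% and 0.80 × 0.85⁵ = 35.5%.
- LCE share 10%: 75.0% and 0.75 × 0.85⁵ = 33.3%.

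The 1-month estimate is too high by the full LCE share, and the 6-month estimate by 2.2 and 4.4 points.

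**The case against.** **The analysis is descriptive, and these patients are visible elsewhere.** SAP 4.4.1.2 plans summaries with 80% CIs and no test. The proportion meeting LCE is a listed outcome (SAP 2.2.5), and SAP 4.4.1.1 adds swimmer and spaghetti plots showing refill times. An LCE patient still eligible for the preceding interval contributes a one-month event there. All of this stands and limits the importance of the point, but none of it corrects the later curves. The two sensitivity analyses in SAP 4.4.1.1 concern time to first refill only.

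**The interval is defined by refill dates, and no refill is given at LCE.** This is fair: the fix makes the event the meeting of the criteria rather than the giving of a refill. But the endpoint as stated is criteria-based. Moreover, under the assumptions of step 6, dropping the rescue censoring and counting the mandatory refill at month 2 gives the same curve from month 2 on (35.5% and 33.3% at 6 months). The overstatement from then on does not depend on this choice.

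**Large LCE shares are hard to reach.** LCE at the first visit of an interval requires that the preceding interval lasted one month. With 20% refilling per month, that is about 20% of patients, or 0.20/(1 − 0.8⁹) = 23% of those refilled within nine months. A share of 20% would need roughly 87% to 100% of them to meet LCE. If a quarter did, which is itself an assumption, the share would be about 5%. That is why the illustration stops at 10%, although patient heterogeneity could raise the share.

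**Stronger inferences to avoid.** A reader might infer that LCE patients are counted as refill-free. They are not: they leave the risk set at rescue and are not carried forward. A reader might also infer that dose contrasts are diluted, most of all at 10 mg/mL. Protocol 3.4.1 does expect trough levels below the efficacious level there. It also allows that the doses may not differ substantially on efficacy because lower doses are refilled more often, and it predicts no LCE rate by arm. The planned pairwise comparisons use time to first refill.

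**Conclusion.** The point holds as a minor correction to an exploratory, descriptive analysis. For the second-to-third and later intervals, the SAP censors LCE patients on a day when the stated endpoint is met, and the refill-free estimates are biased upward wherever LCE occurs. That direction follows from the documents' own thresholds and censoring rule.

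The size does not, because no LCE rate or later refill rate is given. About 3 to 6 points at Month 3 rests on assumed LCE shares of 5% to 10% at the first visit and 20% monthly refilling; with no LCE the bias is zero. Neither direction nor size by arm can be taken from the documents. The first-to-second interval, the primary analysis and its 85-event sizing are untouched.

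**What to change.** In SAP 4.4.1.2, for the second-to-third and later intervals:

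- Count a visit at which LCE criteria, and hence refill criteria, are met as an event, timed from the latest refill.
- Censor at an intravitreal anti-VEGF injection only when the refill criteria were not met at that visit.
- State that the later mandatory refill is not a criteria-based event, and that these patients do not enter later intervals.
- If wanted, keep the current rule as a sensitivity analysis.

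The cost is small. BCVA, CFT, the IxRS refill determination and LCE status are already needed for the study, and patient treatment does not change. The downside is that for these patients the event becomes refill criteria met rather than refill given, which must be labelled, and the later-interval durability estimates become slightly less favourable.

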##### **4.4.2.1 Visual Acuity Change in Best Corrected Visual Acuity (BCVA)**

For change in BCVA from baseline, several supportive preliminary analyses will be performed as described below:

- Change from baseline in BCVA score averaged over Month 9 and Month 10 analyzed with an mixed effects repeated measures (MMRM) model
- Change from baseline in BCVA score averaged over Month 9 and Month 10 analyzed with a trimmed mean approach
- Change from baseline in BCVA score through Month 10 analyzed with an analysis of covariance (ANCOVA) model with missing data imputed by the last observation carry forward (LOCF) approach

- Change from baseline in BCVA score over time through Month 10 for patients treated after surgical Instruction for Use Version 10 (IFU v10) analyzed with descriptive statistics

The details for these analyses are provided as follows:

- Mixed effects with repeated measures (MMRM) analysis for change in BCVA score from baseline averaged over Month 9 and Month 10:

The change from baseline in BCVA score averaged over Month 9 and Month 10 will be compared between each PDS arm and the comparator intravitreal arm using a MMRM model. The model will include the change from baseline at Months 1 to 10 as the response variables and will include the categorical covariates of treatment group, visit, visit-by-treatment group interaction, the continuous baseline value for the response variable (in this case, baseline BCVA), as well as randomization stratification factors as fixed effects. Comparisons between each PDS and the intravitreal arm will be made using a composite contrast over Months 9 and 10. The MMRM model will assume an unstructured covariance structure. If there are convergence problems with the model, then a heterogeneous compound symmetry or a first order autoregressive (AR [1]) covariance structure may be fitted.

Best corrected visual acuity (BCVA) assessments will be censored after the time of rescue intravitreal anti-VEGF injection in the study eye and after the time of explant. Missing data will be implicitly imputed by the MMRM model, assuming a missing at random missing data mechanism (i.e., missing data are dependent on other observed variables but not on the missing data).

An additional MMRM analysis will be performed including all observed measurements. That is, all observed BCVA data will be included regardless of whether patients received rescue treatment or discontinued study treatment due to AE or LCE. Best corrected visual acuity (BCVA) assessments at the time of explant will be censored. This analysis evaluates the treatment policy of PDS with rescue therapy versus the monthly intravitreal ranibizumab.

From the recent end of Phase II meeting with the US FDA on 23 March 2018, the Agency agreed that the change in BCVA from baseline averaged over Month 9 and Month 10 is an appropriate primary endpoint for the Phase III study to assess the non-inferiority (NI) in visual acuity between the Implant and intravitreal arms with an NI margin of 4.5 letters. This NI margin will be used as a reference to assist data interpretation in this preliminary assessment.

To support the interpretation of BCVA change from baseline over time, figures for the adjusted mean change from baseline over time through Month 10 will be provided.

- Trimmed mean analysis for change in BCVA score from baseline averaged over Month 9 and Month 10:

A trimmed mean analysis ([Permutt and Li 2016](#)) will be performed using an analysis of covariance (ANCOVA model) for adjustment for covariates. The dependent variable in the ANCOVA model is the average of Month 9 and Month 10

assessments in change from baseline in BCVA score (if one of the two assessments is missing, the non-missing assessment will be used), and the independent variables are the treatment group, baseline BCVA score (continuous), and the randomization stratification factor of baseline ( $\leq 65$  letters vs.  $\geq 66$  letters) and number of anti-VEGF-intravitreal injections ( $\leq 3$  vs.  $\geq 4$ ).

Patients will be considered to have the worst outcomes and will be trimmed from analysis if any of the following occurs:

- Patients in the PDS arm receive a rescue treatment (intravitreal injection) or undergo explantation prior to Month 9
- Patients in all treatment arms discontinue study treatment due to LCE or AE prior to Month 9
- Patients in all treatment arms have a missing Month 9 assessment and discontinue study treatment due to LCE or AE at Month 9
- Patients in all treatment arms have missing Month 9 and Month 10 assessments and discontinue study treatment due to LCE or AE at Month 10

Such patients will be referred to as "must be trimmed patients." For the remaining patients, if they have Month 9 and/or Month 10 BCVA assessments, they will be considered "completers"; if they have missing Month 9 and Month 10 assessments, the missing data will be considered missing at random, and these patients will be removed from the analysis.

The inferential statistics (i.e., 95% CI) for the trimmed mean will be based on the permutation test. The treatment assignments will be permuted in a sufficiently large random sample of possible ways (~30,000 random samples will be generated).

The algorithm can be stated in the following four steps:

1. Remove patients whose missing assessments are considered missing at random (see definition above) from the analysis.
2. Order the data based on adjusted values from the ANCOVA model, and trim equal fractions (i.e., a pre-specified fraction for fixed trimming) from both treatment arms

The adjusted values are determined as follows. An ANCOVA model as specified above will be fitted for all completers. The estimated treatment effect will be discarded and the coefficients for the covariates will be kept to calculate the adjusted value  $Y - b'X$  for each patient, for which  $Y$  is the change in BCVA score averaged over Month 9 and Month 10,  $X$  is the matrix for the covariates—baseline BCVA score (continuous) and the baseline BCVA score ( $\leq 65$  letters vs.  $\geq 66$  letters) and number of anti-VEGF-intravitreal injections ( $\leq 3$  vs.  $\geq 4$ ), and  $b$  is the estimated coefficient matrix for the covariates.

These adjusted values will be used to rank the data within each treatment group. The "must be trimmed" patients will always be ranked the lowest (regardless of whether their adjusted values are available) and trimmed from

the analyses. The best (1-trimming fraction)\*100% in each group will be used for the analysis specified in Step 3.

3. Refit the ANCOVA model (as specified above) to the trimmed data set, and compute the difference in trimmed mean between two treatment groups.
4. Repeat Steps 2 and 3 on each permuted data to construct a reference distribution for confidence interval estimation for the difference in trimmed mean.

When the proportion of the “must be trimmed” patients in either treatment group in the permuted data exceeds the planned trimmed fraction, the trimming fraction will be chosen adaptively as the greater of the proportions of the “must be trimmed” patients in the two treatment groups.

The percentage of patients to be trimmed will be based on an evaluation of percentage of patients meeting the trimming criteria by Month 9 rounded up to the nearest 5% to avoid many permutation tests from reverting to an adaptive approach. The analysis will be used to assess the difference in BCVA between two treatments excluding the true or assumed worst outcomes. Sensitivity analyses with different choices of trimming percentage may also be conducted.

- Change from baseline in BCVA score through Month 10 analyzed with an ANCOVA model:

The ANCOVA model will include the categorical covariates of treatment group, baseline BCVA score (continuous), and the randomization stratification factors as fixed effects. Separate models will be fit for each pairwise comparison and each study visit. Missing BCVA data, prior to or at Month 10 for each patient, will be imputed using the LOCF approach.

BCVA assessments will be censored after the time of rescue intravitreal anti-VEGF injection in the study eye and after the time of explant. These assessments after initiation of rescue treatment will be imputed using the LOCF approach.

- Descriptive summaries and figures will be provided for change from baseline in BCVA over time through Month 10 for patients treated after IFU Version 10. Observed data will be used. BCVA assessments will be censored after the time of rescue intravitreal anti-VEGF injection in the study eye and after the time of explant.

In addition, a descriptive summary for change from baseline in BCVA over time through the end of the study will be provided. This summary will include all observed data without censoring observations after use of rescue treatment or after explant.

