## **2. STUDY OBJECTIVES**

### **2.1 EFFICACY OBJECTIVES**

The primary efficacy objective for this study is as follows:

- To evaluate the relative efficacy of 10-mg/mL, 40-mg/mL, and 100-mg/mL formulations of ranibizumab, delivered via the Implant, as measured by the time a patient first requires Implant refill according to protocol-defined refill criteria

The secondary efficacy objectives for this study are as follows:

- To evaluate and compare the relative efficacy of 10-mg/mL, 40-mg/mL, and 100-mg/mL formulations of ranibizumab, delivered via the Implant, to that of 10-mg/mL (0.5-mg dose) monthly ITV ranibizumab injections, as measured by the change in BCVA from baseline at Month 9
- To evaluate the efficacy of 10-mg/mL, 40-mg/mL, and 100-mg/mL formulations of ranibizumab, delivered via the Implant, with that of 10-mg/mL (0.5-mg dose) monthly ITV ranibizumab injections over time, as measured by the change in BCVA from baseline over time

- To evaluate the efficacy of 10-mg/mL, 40-mg/mL, and 100-mg/mL formulations of ranibizumab, delivered via the Implant, with that of 10-mg/mL (0.5-mg dose) monthly ITV ranibizumab injections over time, as measured by the change in central foveal thickness (CFT, defined as the retinal thickness in the center of the fovea) from baseline over time
- To evaluate the functionality of the Implant by assessing that there is no evidence of Implant clogging in more than 10% of patients in the Implant arms at Month 9

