### **2.2.2 Secondary Efficacy Outcome Measures**

The secondary efficacy outcome measures are as follows:

- Change from baseline in BCVA at Month 9
- Average change from baseline in BCVA over time
- Change from baseline in BCVA over time

- Change from baseline in CFT over time, as assessed on SD-OCT by the central reading center
- Occurrence of Implant clogging

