#### **4.4.2.2 Anatomical Outcomes**

The change in CFT (with and without inclusion of pigment epithelium thickness and its elevation in the foveal center, as assessed by the Reading Center) from baseline at Month 9 will be compared between each PDS arm and the intravitreal arm using the same analysis method (MMRM) and data handling rules that are used for the change from baseline in BCVA score at the average of Month 9 and Month 10. Comparisons between the Implant arms and the intravitreal arm will be made using a contrast at Month 9. Figures for adjusted mean change from baseline in CFT over time through Month 9 will be provided. Descriptive summaries for change from baseline in CFT through Month 9 will also be provided. Data for patients who receive rescue treatment or undergo explantation prior to Month 9 will be censored.

In addition, a descriptive summary for change from baseline in CFT over time through the end of the study will be provided. This summary will include all observed data without censoring observations after use of rescue treatment or after explant.

Changes from screening in total lesion area, area of CNV lesion, and CNV leakage over time through Month 9, as assessed by fluorescein angiography, as well as changes in CNV perfusion over time through Month 9, as assessed by OCT angiography will be summarized using descriptive statistics. Data for patients who receive rescue treatment or undergo explantation prior to Month 9 will be censored. Missing data will not be imputed.

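### For BCVA change at Month 9, the only model-based Implant-versus-intravitreal difference that the SAP spells out is the LOCF ANCOVA; the MMRM contrast is set only for the Month 9/10 average

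*SAP*

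**What the plan says.** Protocol 2.1 makes comparison of each Implant arm with monthly intravitreal ranibizumab a secondary objective, "as measured by the change in BCVA from baseline at Month 9". SAP 2.2.2 keeps this as the first secondary outcome: "Change from baseline in BCVA at Month 9".

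SAP 4.4.2.1 lists four supportive BCVA analyses:

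- **MMRM.** "The model will include the change from baseline at Months 1 to 10 as the response variables", with a visit-by-treatment interaction. The between-arm comparison is then fixed: "Comparisons between each PDS and the intravitreal arm will be made using a composite contrast over Months 9 and 10". There are two versions, one censoring BCVA after rescue or explant and one using all observed data apart from a rule at explant. Also planned: "figures for the adjusted mean change from baseline over time through Month 10 will be provided".
- **Trimmed mean.** The dependent variable is the Month 9/10 average.
- **ANCOVA by visit.** "Separate models will be fit for each pairwise comparison and each study visit". For missing values: "Missing BCVA data, prior to or at Month 10 for each patient, will be imputed using the LOCF approach". Assessments after rescue or explant are censored, and the last earlier value stands in for them.
- **Descriptive summary** for patients treated under the later surgical instructions (IFU version 10).

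The section also plans an observed-data summary of BCVA change through the end of the study. For CFT, SAP 4.4.2.2 uses the same kind of model but a different target: "Comparisons between the Implant arms and the intravitreal arm will be made using a contrast at Month 9".

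**The concern.** The Month 9 objective is comparative, so it needs a difference between arms with an interval. Both non-LOCF models that compare arms in 4.4.2.1 are aimed at the Month 9/10 average, a target tied to the Phase III discussion. That leaves the by-visit ANCOVA with LOCF as the only named model for the Month 9 difference.

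Two features make it a weak choice for that role. LOCF assumes that vision stays fixed at the last retained value. In addition, rescue (Protocol 5.1.1.2 and the rescue criteria in SAP section 2) and explantation are defined only for Implant patients, so the rule that replaces later scores with pre-rescue or pre-explant ones acts on one side of the comparison. The documents do not allow the direction or size of any resulting bias to be stated. The SAP amendment rationale also says that LOCF will no longer be the primary imputation method, which suggests that this role was not intended.

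**Working it through.** **1. Which outputs cover Month 9 BCVA, and which give a specified model-based difference with a CI?**

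| Analysis | Covers Month 9? | Specified model-based Month 9 difference with CI? |
|---|---|---|
| MMRM contrast, both versions | Only within the Month 9/10 average | No |
| MMRM adjusted-mean figures through Month 10 | Yes | No; figures of means |
| Trimmed mean | Only within the Month 9/10 average | No |
| By-visit ANCOVA with LOCF | Yes | Yes |
| Observed-data descriptive summaries | Yes | No model named |

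**2. Is the Month 9 contrast available from the specified MMRM?** Write d9 and d10 for the Implant-minus-intravitreal differences at the two visits. The contrast for the average is (d9 + d10)/2. Because the model has a visit-by-treatment interaction and includes Month 9, d9 is already estimated. No new model is needed.

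**3. Precision.** Inputs from SAP 2.3: SD 10 letters, 60 patients per Implant arm, 40 in the intravitreal arm, and a stated two-sided 80% CI half-width of about 2.62 letters.

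- Root term: sqrt(1/60 + 1/40) = 0.2041.
- Stated figure: 1.2816 × 10 × 0.2041 = 2.616 letters, which reproduces 2.62. A single arm of 40 would give 2.03, so the plan's figure is for the between-arm difference.
- Month 9 alone at the 95% level that SAP 4.4 adopts, with no missing data: 1.960 × 10 × 0.2041 = 4.00 letters.
- With 8% loss in each arm (the rate the device plan, Protocol Appendix 21 section 7.4, assumes for its clogging analysis), n = 55.2 and 36.8: 1.960 × 10 × sqrt(1/55.2 + 1/36.8) = 4.17 letters.
- Month 9/10 average: 4.00 × sqrt((1 + r)/2), where r is the correlation between the two visits. The documents do not give r. Assuming 0.6 gives 3.58; assuming 0.9 gives 3.90.

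With complete data, the single-visit contrast costs about 0.1 to 0.4 letters of half-width. These are normal-approximation figures without covariate adjustment. They show feasibility and do not predict the trial's intervals.

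**4. Timing.** SAP 2.4 places the primary analysis after the last patient's Month 9 visit. If the BCVA analyses use that same cut, the latest-enrolled patients may have no Month 10 value. The average would then lean partly on the model at Month 10, whereas Month 9 is the visit the cut-off was built around.

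**The case against.** A reader might infer that Month 9 BCVA is estimated by LOCF alone, or that the MMRM yields nothing but the composite contrast. The documents do not support either reading. SAP 4.4 makes observed data the default, SAP 4.4.2 promises descriptive summaries of every secondary endpoint, and 4.4.2.1 adds the uncensored observed-data summary and the MMRM adjusted-mean figures. SAP 4.4.2 also promises a difference with a 95% CI for outcome measures between each Implant arm and the intravitreal arm. On a fair reading this could cover an observed-data Month 9 difference. It names no model, so the choice stays open.

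A reader might also infer that the Month 9 outcome was swapped for a new one after the unmasked interim analysis of October 2017. That does not hold either. SAP 2.2.2 retains the Month 9 outcome. By-visit pairwise ANCOVA with LOCF is broadly the method of Protocol 6.4.2, now with a continuous baseline covariate and a censoring rule. The Month 9/10 average is presented openly as preliminary and aligned with Phase III.

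Finally, the body of the SAP does not rank the BCVA methods; the statement about LOCF stands in the amendment rationale. The Month 9/10 average contains Month 9, and nothing in the documents shows that the two estimates would differ materially. All of this lowers the weight of the point. What stands is that the comparative objective at Month 9 has one explicitly specified model-based answer, and it uses LOCF.

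**Conclusion.** The point holds as a minor gap in specification. No decision rule in the documents depends on the missing contrast, the study is exploratory, and SAP 4.4.2 rules out formal testing of BCVA between the Implant and intravitreal arms. The gap is still worth closing: the outcome is listed, its objective is comparative, and the parallel CFT analysis already has the contrast.

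Preferring the MMRM rests on its missing-at-random assumption, which is itself doubtful when values are censored at rescue. Showing the all-observed version beside the censored one makes that dependence visible. The effect on the estimated difference cannot be given from the documents. The precision cost of about 0.1 to 0.4 letters rests on SD 10, full enrolment, complete data and an assumed correlation of 0.6 to 0.9.

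**What to change.** In SAP 4.4.2.1, add the Month 9 Implant-versus-intravitreal contrast with its 95% CI from the MMRM already specified, in both the rescue-censored and the all-observed versions. Name it as the main estimate for the Month 9 secondary outcome. Keep the by-visit LOCF ANCOVA as a sensitivity analysis and the Month 9/10 average as the supportive analysis aligned with Phase III. The cost is one extra contrast per model version and the matching table rows; no new data or model is needed. Because interim results had been seen before this amendment, record the date and reason for the addition.
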